### **Ibrutinib:**

During Phase 1 and Phase 2 when loncastuximab tesirine is given intermittently, ibrutinib will be dispensed 560 mg orally once daily during all cycles. Relative dose intensity (%) for ibrutinib is calculated as  $100 * [\text{total dose received (mg)} / \text{duration of treatment (days)} * 560 (\text{mg/day})]$

During Phase 2 when loncastuximab tesirine is given at every cycle, ibrutinib will be dispensed 560 mg/day orally once daily beginning C1D1 for C1 and C2, then reduced to 420 mg/day orally once daily at C3D1 and for all subsequent cycles. Relative dose intensity (%) for ibrutinib is calculated as  $100 * [\text{total dose received (mg)} / \{\text{duration of treatment (days)} \text{ in C1 and C2} * 560 (\text{mg/day}) + \text{duration of treatment (days) in all subsequent cycles} * 420 (\text{mg/day})\}]$

Duration of treatment, number of cycles dosed, total dose received (mg), average dose per cycle (mg), and relative dose intensity for ibrutinib will be summarized.

Exposure data and infusion details in both loncastuximab tesirine and ibrutinib will be listed.

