A two-stage design with futility monitoring will be used for this new Phase 2 cohort. In the first stage, 60 patients will be accrued. If there are 20 or fewer CRs in these 60 patients, this cohort will be stopped. Otherwise, 40 additional patients will be accrued for a total of 100.

The study will include a Screening Period (of up to 28 days), a Treatment Period (cycles of 3 to 4 weeks), and a Follow-up Period (approximately every 12-week visits for up to 2 years after treatment discontinuation). On March 3, 2022, ADC Therapeutics announced to discontinue the study. The new Phase 2 cohort will be not enrolled.

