## 4.1 Sample Size Consideration

There will be 136 patients for the entire study.

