### Phase 1:

47 patients will be treated with the combination of loncastuximab tesirine and ibrutinib.

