## **5.8 Exposure to Treatment**

### **5.8.1 Extent of Study Drug Exposure**

Study drug exposures will be based on the Safety Analysis Set.

A treatment cycle is defined as 3 weeks (i.e., 21 days) for Cycle 1 and Cycle 2, and then 4 weeks (i.e., 28 days) for subsequent cycles.

Duration of treatment (days) for loncastuximab tesirine, ibrutinib and both is calculated as date of last treatment – date of first treatment + 1.

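### SAP 5.8.1: the ibrutinib relative dose intensity formula that applies to all treated patients lacks brackets round its denominator, so as written it multiplies by 560 instead of dividing (low priority; the intended form is evident)

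*SAP*

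**What the plan says.** The Ibrutinib part of SAP 5.8.1 gives two formulas for relative dose intensity, each expressed as a percentage.

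- **Phase 1 and intermittent Phase 2.** The scope is set by this sentence: "During Phase 1 and Phase 2 when loncastuximab tesirine is given intermittently, ibrutinib will be dispensed 560 mg orally once daily during all cycles". The formula follows directly. The words that lead into it are "ibrutinib will be dispensed 560 mg orally once daily during all cycles. Relative dose intensity (%) for ibrutinib is calculated as", and it then reads: "100 * [\text{total dose received (mg)} / \text{duration of treatment (days)} * 560 (\text{mg/day". The typesetting commands in that last quote come from the machine-read copy. The closing bracket follows at once, with no inner bracket or brace anywhere in the expression.
- **Every-cycle Phase 2.** The denominator is the sum of two products, days in Cycles 1 and 2 at 560 mg/day plus later days at 420 mg/day. The whole sum stands inside braces. Its last term reads "duration of treatment (days) in all subsequent cycles} * 420 (\text{mg/day".

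The opening of SAP 5.8.1 defines the time term for both: "Duration of treatment (days) for loncastuximab tesirine, ibrutinib and both is calculated as date of last treatment – date of first treatment + 1". Relative dose intensity is a planned output. Protocol 9.6 calls for it, and SAP 5.8.1 lists it among the ibrutinib summaries.

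On who is covered, SAP section 4 says of the every-cycle cohort: "The new Phase 2 cohort will be not enrolled". SAP 4.1 gives the total: "There will be 136 patients for the entire study".

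**The concern.** A formula in an analysis plan should be programmable as it stands. Division and multiplication have equal rank and run left to right in ordinary arithmetic and in SAS, which SAP section 5 names as the analysis software. Coded literally, the first formula gives a quantity that is neither a percentage nor dimensionless. The two formulas in the same subsection then treat one variable in incompatible ways, and the correctly written one applies to nobody.

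What is at stake is narrow but real. The ibrutinib list in SAP 5.8.1 covers duration, cycles dosed, total dose, average dose per cycle and relative dose intensity. Unlike the loncastuximab tesirine list, it has no line for delays, reductions and interruptions. Within that section, relative dose intensity is therefore the only ibrutinib measure that sets dose received against dose planned.

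**Working it through.** The SAP states no numerical value of relative dose intensity, so there is no figure to reproduce. The check is to evaluate the formula as written and with the denominator grouped.

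**Inputs**
- D = total ibrutinib dose received, in mg.
- T = days from first to last treatment inclusive (SAP 5.8.1).
- Planned dose rate = 560 mg/day (SAP 5.8.1).
- Illustrative assumptions, not from the documents: T = 42, 98 or 365 days, with 100% or 75% of the planned dose taken.

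**Formulas**
- As written, left to right: 100 × (D / T) × 560.
- With the denominator grouped: 100 × D / (T × 560).

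| T (days) | Share of planned dose | D (mg) | As written | Grouped |
|---|---|---|---|---|
| 42 | 100% | 23,520 | 31,360,000 | 100 |
| 42 | 75% | 17,640 | 23,520,000 | 75 |
| 98 | 100% | 54,880 | 31,360,000 | 100 |
| 98 | 75% | 41,160 | 23,520,000 | 75 |
| 365 | 100% | 204,400 | 31,360,000 | 100 |
| 365 | 75% | 153,300 | 23,520,000 | 75 |

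For example, at 98 days and full dose, 54,880 / 98 = 560, and 100 × 560 × 560 = 31,360,000. Grouped, 98 × 560 = 54,880, and 100 × 54,880 / 54,880 = 100.

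**Size of the discrepancy.** The ratio of the two forms is [100 × D × 560 / T] / [100 × D / (T × 560)] = 560² = 313,600. D and T cancel, so the factor is the same for every patient.

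**Units.** As written, (mg / day) × (mg/day) = mg²/day². Grouped, mg / (day × mg/day) has no unit, as a percentage requires.

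**Every-cycle formula.** For 42 days at 560 mg and 56 days at 420 mg, all taken, D = 23,520 + 23,520 = 47,040 mg. The braced denominator is also 47,040, so the result is 100%. That formula is sound.

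**Patients covered.** SAP 4.1 gives 47 in Phase 1 ("47 patients will be treated with the combination of loncastuximab tesirine and ibrutinib") and 89 in Phase 2, made up of 49 non-GCB DLBCL, 30 GCB DLBCL and 10 MCL: 49 + 30 + 10 = 89, and 47 + 89 = 136. All fall under the ungrouped formula.

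**The case against.** The strongest reply is that this is a typographical slip with only one sensible reading. The quantity is called a percentage, 560 carries the unit mg/day, and the neighbouring formula shows the same ratio with its denominator in braces. A literal result in the tens of millions would be seen at once, so it could not pass unnoticed into a report as a modest bias could. No endpoint, test, stopping rule or error rate uses it. All of this stands and sets the priority. It does not make the written formula right.

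A second reply is that the grouping may have been lost when the PDF was read. That cannot be wholly excluded without the original page. It is unlikely, because the formula is set inline with a slash, its outer square brackets survived, and so did the braces of the neighbouring formula.

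Two stronger readings are tempting, and the documents support neither.

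- A reader might infer that the study's account of ibrutinib tolerability is compromised. The Phase 1 primary endpoints in Protocol section 3 are adverse events, dose-limiting toxicities, interruptions and reductions, and changes in safety measurements. SAP 5.10.1.1 separately summarises events leading to ibrutinib delay, reduction, interruption or discontinuation. None of these uses the formula.
- A reader might say that every enrolled patient is affected. SAP 5.2 counts anyone who signed consent as enrolled, including screen failures, whereas exposure is summarised on the Safety Analysis Set. The right term is treated patients.

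The total of 136 also needs a caveat. SAP 4.1 still carries a sentence about accruing roughly 100 every-cycle patients, and gives both 49 and about 48 for the non-GCB cohort. The 136 excludes the former and matches 49. With 48 it would be 47 + 48 + 30 + 10 = 135. Neither changes which formula applies.

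**Conclusion.** The formula is wrong as written. Followed literally, it overstates ibrutinib relative dose intensity by a factor of 313,600 for all treated patients in Phase 1 and the intermittent Phase 2 cohorts. On the SAP's own account, that is everyone treated. The conclusion assumes ordinary left-to-right evaluation, a faithful copy of the SAP's brackets, and no enrolment to the every-cycle cohort.

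The practical weight is low. The intended form is evident from the same subsection, the affected output is a descriptive exposure summary, and an implausible value would very probably be caught. This is an editorial correction to a stated analysis rule. It gives no reason to doubt any efficacy or safety conclusion.

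**What to change.** In SAP 5.8.1, group the denominator of the formula for Phase 1 and intermittent Phase 2, in the style already used for the every-cycle cohort:

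100 × [total dose received (mg) / {duration of treatment (days) × 560 (mg/day)}]

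This costs one pair of braces. It needs no new data, changes no planned dose and adds no analysis. If the exposure tables are already programmed, confirm that the code groups the denominator. A patient who took every planned dose should return 100, and one who took three quarters should return 75.

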### **5.8.2 Subsequent Anticancer Therapy or Procedure**

Patients' subsequent anticancer therapies or procedures including systemic therapy, radiation, transplant, or other, along with the start date of new anticancer therapy or procedure will be listed.

### **5.9 Efficacy Analyses**

Efficacy analyses will be based on the Efficacy Analysis Set. Primary efficacy analyses will also be based on Per Protocol Set.

Primary efficacy analyses will be based on CRR according to the 2014 Lugano classification (Cheson et al., 2014) as determined by independent review committee (IRC) in all DLBCL patients given loncastuximab tesirine at every cycle in combination with ibrutinib.

All efficacy endpoints and tumor assessment data will be listed.

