9.2 Analysis Populations

- The Safety population will consist of all patients who receive study drug.
- The DLT-evaluable population will consist of all patients in Phase 1 dose escalation, who receive study drugs, and will exclude patients who discontinue from the study during the DLT Period without experiencing a DLT.
- The Efficacy population will consist of all patients who receive at least 1 dose of study drug, who have valid baseline disease assessment(s), and who have at least one valid post-baseline disease assessment. Patients who do not have a post-baseline assessment due to early clinical progression or death (after receiving study drug) will also be included.
- The PK population will consist of all patients who have at least 1 pre-(C1D1) and 1 post-dose valid PK assessment.
- [REDACTED]
- Per Protocol population: All patients in the Safety population without major protocol deviations, which will be further described in detail in the SAP.

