Phase 2:	
Phase 2:
 
ORR according to the 2014 Lugano classification in the non-GCB DLBCL, GCB DLBCL, all DLBCL, and MCL patients. ORR defined as the proportion of patients with a BOR of CR or PR for all treated patients.
 
ORR is determined by IRC and/or Investigator.
 
CRR according to the 2014 Lugano classification(Cheson et al., 2014) as determined by IRC and/or Investigator in the non-GCB DLBCL, GCB DLBCL, all DLBCL, and MCL patients
 
CRR according to the 2014 Lugano classification(Cheson et al., 2014) as determined by investigator in the non-GCB DLBCL patient
 
Frequency and severity of AEs and SAEs in the non-GCB DLBCL, GCB DLBCL, all DLBCL, and MCL patients
 
Change from baseline of safety laboratory values, vital signs, ECOG performance status, and 12-lead ECGs in the non-GCB DLBCL, GCB DLBCL, all DLBCL, and MCL patients
 
Change from baseline in PROs as measured by the European Organization for Research and Treatment of Cancer (EORTC) QLQ-C30, LymS of FACT4-y, and EQ-5D-5L, in the non-GCB DLBCL, GCB DLBCL, all DLBCL, and MCL patients

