## 5 Statistical methods

All analyses will use SAS® version 9.4 or higher.

Unless otherwise stated, tables, listings, and figures will be broken down by cohort (non-GCB DLBCL, GCB DLBCL, all DLBCL and MCL). Additional tables include Phase 1 tables by dose level for safety, demographic and dosing, Phase 1 tables by dose level for dose escalation patients only, and tables of 60 µg/kg and 75 µg/kg loncastuximab tesirine in both Phase 1 and 2 by cohort. Tables and figures are based on the defined analysis population.

Categorical data will be presented using counts and percentages, with the number of patients in the analysis population as the denominator for percentages. Percentages will be rounded to 1 decimal place and not be displayed for zero counts.

Continuous data will be summarized using the number of observations (n), mean, standard deviation (std), median, minimum, and maximum. Minima and maxima will be rounded to the precision of the original value, and means, medians, and 95% confidence intervals (CIs) if presented will be rounded to 1 decimal place greater than the precision of the original value. The std will be rounded to 2 decimal places greater than the precision of the original value, up to a maximum of 3 decimal places.

CI will be two-sided and use  $\alpha=0.05$  (i.e., 95% CIs), unless otherwise specified. For exact estimates, the CI will be calculated using the Clopper-Pearson exact method. For Kaplan-Meier estimates, the CI will be calculated using the Greenwood's formula with (complementary) log-log transformation.

Kaplan-Meier plots will be provided along with Kaplan-Meier estimates.

The Baseline value is defined as the last non-missing value or measurement taken prior to the first dose of study drug.

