### 5.1 Analysis Populations

#### 5.1.1 Safety Analysis Set

All patients who receive study drugs.

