#### 5.1.3 Efficacy Analysis Set

All patients who receive at least 1 dose of study drugs, have valid baseline disease assessment(s), and have at least one valid post-baseline disease assessment. Patients who do

not have a post-baseline assessment due to early clinical progression or death (after receiving study drugs) will also be included.

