### **5.9.2 Overall Response Rate**

Overall response rate (ORR) is defined as the proportion of patients with a BOR of CR or partial response (PR). ORR is according to the 2014 Lugano classification as determined by IRC (Phase 2 only) and the investigator (both Phase 1 and Phase 2).

For the analysis of ORR,

- The category of BOR includes complete response (CR), partial response (PR), stable disease (SD), progressive disease (PD), and inevaluable (NE).
- Overall responses derived for BOR must be assessed on or before the start of subsequent anti-cancer therapy or procedure.
- A BOR of SD requires the patient on-study for a minimum of 35 days after the first dose of study drug. A patient with SD only before this time will be considered as NE.
- For patients who do not have post-baseline assessment due to early clinical progression or death (after receiving study drug), they will be categorized separately from patients with assessments.

Disease control rate (DCR) is defined as the proportion of patients with a BOR of CR, PR, or SD.

The ORR and DCR and their 95% two-sided exact CIs will be presented by the IRC and the investigator, respectively.

Percent change from baseline in the sum of product of the perpendicular diameters (SPD) for target lesions will be presented and also displayed as a waterfall plot, with vertical bars representing the sorted values of best percent reduction for each patient.

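### Phase 2 ORR is defined for all treated patients, but the SAP computes it on the Efficacy Analysis Set, which leaves some treated patients out of the denominator

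*SAP*

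**What the plan says.** The endpoint table in SAP section 3 gives, for Phase 2, "ORR defined as the proportion of patients with a BOR of CR or PR for all treated patients". Protocol Table 3 carries the same sentence.

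The analysis sections use a different population. SAP 5.9 states "Efficacy analyses will be based on the Efficacy Analysis Set", and SAP section 5 has categorical data presented "with the number of patients in the analysis population as the denominator for percentages". To enter the Efficacy Analysis Set a patient must have been dosed, have a valid baseline assessment "and have at least one valid post-baseline disease assessment" (SAP 5.1.3). The one exception is a post-baseline assessment missing because of early clinical progression or death. Protocol 9.2 has the same rule: patients "who have valid baseline disease assessment(s), and who have at least one valid post-baseline disease assessment", with the same exception.

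The set that matches the endpoint definition already exists. It is the Safety Analysis Set, "All patients who receive study drugs" (SAP 5.1.1), but it is not assigned to ORR.

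SAP 5.9.2 lists a not-evaluable (NE) category for best overall response. It adds that patients unassessed because of early progression or death "they will be categorized separately from patients with assessments".

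**The concern.** The same endpoint has two denominators, and nothing says which one governs. A programmer working from SAP section 3 and one working from SAP 5.9 could report different ORRs from the same data.

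The difference is not neutral. A treated patient with no post-baseline assessment has no response on record and cannot be in the numerator. Removing that patient shrinks the denominator only, so ORR rises or stays the same. In a single-arm study whose Phase 2 efficacy results are response rates with confidence intervals, the denominator should be the one that defines the endpoint.

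**Working it through.** **Step 1. Who falls between the two definitions?**

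| Treated patient | All treated (SAP 3, Protocol Table 3) | Efficacy Analysis Set (SAP 5.1.3) |
|---|---|---|
| Valid baseline and at least one valid post-baseline assessment | in | in |
| No post-baseline assessment, early clinical progression or death | in | in, by the exception |
| No post-baseline assessment, any other reason | in | out |
| No valid baseline | in | out |

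The third row can occur. Under Protocol 7.2 no further data are collected once consent is withdrawn, and Protocol 7.3 covers loss to follow-up. Either can happen before the Week 6 scan. The fourth row should be nearly empty, because Protocol 5.1 requires measurable disease and Protocol 8.1 requires baseline imaging within 4 weeks before the first dose.

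**Step 2. Does SAP 5.9.2 put them back?** No. The NE category and the separate early-progression/death category classify patients who are already in the analysis set. They do not admit anyone whom 5.1.3 has excluded.

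**Step 3. Is the SAP consistent elsewhere?** Not fully. SAP 5.9.5 censors at first dose those patients who have no post-baseline tumor assessment and no progression or death. Under 5.1.3 such patients are already outside the set, so under 5.9 as written that rule has nobody to act on.

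**Step 4. Reproduce the only Phase 2 ORR figures given (Protocol 2.2).** Non-GCB: 10/22 = 45.5%. The GCB interim denominator is not stated. Both 10/13 and 20/26 give 76.9%, but only 13 fits the combined rate: (10+10)/(22+13) = 20/35 = 57.1%, whereas (10+20)/(22+26) = 30/48 = 62.5%. All three stated ORRs are reproduced with 22 and 13.

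**Step 5. Size per omitted patient.** Cohort sizes are from SAP 4.1: 49 non-GCB (the same bullet also says approximately 48), about 30 GCB, and 49 + 30 = 79 for all DLBCL. The interim rates are scaled to these sizes and treated as all-treated rates. Both steps are assumptions, because Protocol 2.2 does not say which population the interim rates used. Responders: 0.455 × 49 = 22.3, taken as 22; 0.769 × 30 = 23.1, taken as 23; together 45.

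With x responders, N treated and k omitted for no post-baseline assessment, the rise is x/(N − k) − x/N. The number k is not in the documents; 0, 1 and 2 are shown.

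| Cohort | k = 0 (exact 95% CI) | k = 1 | k = 2 |
|---|---|---|---|
| Non-GCB | 22/49 = 44.9% (30.7 to 59.8) | 22/48 = 45.8%, +0.9 | 22/47 = 46.8%, +1.9 |
| GCB | 23/30 = 76.7% (57.7 to 90.1) | 23/29 = 79.3%, +2.6 | 23/28 = 82.1%, +5.5 |
| All DLBCL | 45/79 = 57.0% (45.3 to 68.1) | 45/78 = 57.7%, +0.7 | 45/77 = 58.4%, +1.5 |

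The intervals are 29.1, 32.4 and 22.8 points wide.

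**Step 6. Patients with no valid baseline.** Here the direction is not fixed. Dropping one non-GCB patient takes ORR from 44.9% to 21/48 = 43.8% if that patient was a responder, or to 22/48 = 45.8% if not.

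**The case against.** The best case for leaving the plan alone runs as follows. ORR is a secondary Phase 2 endpoint, reported as an estimate with a confidence interval and no test. The all-treated wording appears only in the two endpoint tables; it is absent from the protocol synopsis, Protocol 9.7.2 and SAP 5.9.2. The study was discontinued and the every-cycle cohort was not enrolled. The exception in 5.1.3 already keeps the unassessed patients most likely to be treatment failures, so few or none may be lost. All of this stands, and it holds the point to minor. It does not remove the conflict, since the same defining sentence is in both documents and no text ranks it below SAP 5.9.

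A reader might infer more than the documents support:

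- *That SAP 4.3, which records no modification to the protocol's statistical section, is wrong.* It is not. Protocol 9.2 and SAP 5.1.3 define the same population.
- *That CRR, DCR and OS are contradicted too.* No text gives any of them an all-treated denominator. The upward effect of omitting unassessed patients applies to CRR as well, but that is a matter of choice of set and not a contradiction.
- *That patients who switch to another anticancer therapy, or stop for toxicity, before a first scan are generally lost.* Protocol 4.4 asks for the end-of-treatment visit before new therapy, and Table 2 schedules a disease assessment at that visit for patients stopping for reasons other than progression. Patients who stop for toxicity are also due follow-up imaging under Protocol 8.1.
- *That the inflation is large.* Exclusion shares of 5% to 15% would give rises of roughly 3 to 10 points, but nothing in the documents supports such shares for this study.

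**Conclusion.** The contradiction is real and in current text: Phase 2 ORR as defined and Phase 2 ORR as it would be programmed have different denominators. For patients with no post-baseline assessment, the error can only run upward. Its size is unknown and may be zero. On the assumption that the interim rates are all-treated rates at the SAP cohort sizes, it is about 0.9 (non-GCB), 2.6 (GCB) and 0.7 (all DLBCL) points per omitted patient, well inside the sampling uncertainty.

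No stated decision depends on it. Both two-stage rules use counts of complete responses, and the cohort carrying the primary endpoint was not enrolled. Severity: minor.

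**What to change.** Change the SAP only, in 5.9 and 5.9.2:

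- Make the Safety Analysis Set, by cohort, the denominator for Phase 2 ORR.
- Count treated patients with no post-baseline assessment as NE, hence non-responders, and report their number and reasons.
- Report separately how many patients, if any, lack a valid baseline, and say how their best response is assigned.
- Keep ORR on the Efficacy Analysis Set as a labelled supportive analysis.

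CRR and DCR come from the same best-response table, so showing them on the same denominator is advisable for consistency, although the documents do not require it. OS needs no change, and neither do Protocol 9.2 and 9.7.

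Deleting the all-treated wording would also end the contradiction. It would leave the upward effect in place, however, and would mean editing the endpoint definition in Protocol Table 3 as well.

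The cost is a few lines of SAP text and one extra set of response-rate outputs (IRC and investigator, by cohort). No new data are needed. The reported rates may come out slightly lower.

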## 1 Introduction

This statistical analysis plan (SAP) describes the statistical methods to be used during the reporting and analysis of data collected under ADC Therapeutics Protocol ADCT-402-103.

This SAP should be read in conjunction with the study protocol and case report form (CRF). This version of the plan has been developed using the Protocol Amendment 5 dated 31 August 2021.

Since this study was early terminated due to lack of efficacy singnal. The current number of patients will be reduced in Phase 1 dose escalation , Phase 1 does expansion, and Phase 2.

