## **Phase 2:**

89 patients will be treated during Phase 2 study.

The 89 patients will be treated with the combination of loncastuximab tesirine and ibrutinib in three different cohorts:

- 49 Non-GCB DLBCL was to enroll and treated interim data analysis for futility. The study will close with approximately 48 patients.
- GCB DLBCL cohort will enroll approximately 30 patients, and
- MCL cohort will enroll approximately 10 patients

Approximately 100 R/R DLBCL patients with at least 40 patients each for GCB and non-GCB will be accrued to the new treatment cohort where loncastuximab tesirine is given at every cycle with ibrutinib po daily.

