### **Phase 2 Sample Size Justification for the non-GCB DLBCL Cohort Where Loncastuximab Tesirine is Given Intermittently in Combination with Ibrutinib**

The primary hypothesis is that the CRR based on central review for patients treated with loncastuximab tesirine and ibrutinib is significantly greater than 20% (i.e.,  $H_0: p \leq 0.2$  vs.  $H_a: p > 0.2$ ). This hypothesis will be tested at type I error of 0.05 (two sided).

Simon's 2-stage design (Simon, 1989) will be used for Phase 2 non-GCB DLBCL cohort. The null hypothesis that the true CRR is 0.2 will be tested against a one-sided alternative. In the first stage, 22 patients will be accrued. If there are 5 or fewer CRs in these 22 patients, this cohort will be stopped. Otherwise, 44 additional patients will be accrued for a total of 66. The null hypothesis will be rejected if 20 or more CRs are observed in 66 patients. This design yields a type I error rate of 0.05 and power of 90% when the true CRR is 0.4.

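### The Phase 2 primary efficacy analysis is defined on a cohort that was never enrolled, and the data-cut and non-GCB test rules need 66 patients from a cohort closed at 48 or 49

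*SAP*

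**What the plan says.** **Primary analysis.** SAP section 5.9 rests the primary efficacy analysis on CRR by the "independent review committee (IRC) in all DLBCL patients given loncastuximab tesirine at every cycle in combination with ibrutinib". It adds: "Primary efficacy analyses will also be based on Per Protocol Set".

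**Enrolment.** Section 1 discloses the termination: "Since this study was early terminated due to lack of efficacy singnal". Section 4 gives the discontinuation date, 3 March 2022, and says: "The new Phase 2 cohort will be not enrolled". Section 4.1 states "There will be 136 patients for the entire study", made up of 47 in Phase 1 and 89 in Phase 2.

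**Text left unchanged.** The same section 4.1 still says: "Approximately 100 R/R DLBCL patients with at least 40 patients each for GCB and non-GCB will be accrued to the new treatment cohort". Sections 4.1 and 6 keep that cohort's 60-patient futility look, and section 4.1 keeps its test at 40 CRs in 100.

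**Non-GCB cohort.** Section 4 closes enrolment to the intermittent-dosing non-GCB cohort. Section 4.1 gives its size as 49 and then says: "The study will close with approximately 48 patients". It still calls the non-GCB hypothesis primary and keeps its decision rule: "The null hypothesis will be rejected if 20 or more CRs are observed in 66 patients". Section 3 lists non-GCB CRR among the secondary endpoints. Section 7 allows a snapshot for the primary and key secondary endpoints once 66 Phase 2 non-GCB patients have six months of follow-up after first response. Section 4.3 records no modification to the protocol's statistical section.

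**The concern.** The SAP was written knowing that the study had stopped. Its totals were cut from the protocol's 243 to 136, but its analysis rules were not changed to match. Followed literally, section 5.9 produces a Phase 2 primary table and a per-protocol repeat with no patients.

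At stake is a defined primary claim and a usable data cut. With the every-cycle cohort gone, the leftover non-GCB rule is the only Phase 2 test that could still be applied, and the SAP calls that hypothesis primary in one place and lists the endpoint as secondary in another. No cut-off is given for 48 or 49 patients. Any cut-off set now would be chosen after the April 2021 interim result, 6 CRs in the first 22 non-GCB patients (Protocol section 2.2), was known.

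**Working it through.** **1. Who is in the primary analysis?** Counts from SAP section 4.1:

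- Phase 2: 49 non-GCB + 30 GCB + 10 MCL = 89, all on intermittent dosing.
- Whole study: 47 + 89 = 136, which leaves 136 − 136 = 0 for the every-cycle cohort, against 100 planned.
- If the retained accrual sentence were true, the total would be 136 + 100 = 236, contradicting 136.

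No other patients fit the definition. The Phase 1 schedule in SAP sections 4 and 5.8.1 gives loncastuximab tesirine in cycles 1 and 2, and optionally 5 and 6.

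**2. The 66-patient snapshot.** 66 − 49 = 17 and 66 − 48 = 18, so the condition is 17 or 18 patients short in a closed cohort.

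**3. The non-GCB rejection rule.** Inputs from SAP section 4.1: first stage of 22, continue with at least 6 CRs, reject with at least 20 of 66, null CRR 0.20, alternative 0.40. For total size n and cut-off r, with X1 ~ Bin(22, p) and X2 ~ Bin(n − 22, p):

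P(reject) = Σ over x = 6 to 22 of P(X1 = x) · P(X2 ≥ r − x)

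The plan's design comes first, then the sizes that exist:

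| n | r | One-sided alpha (CRR 0.20) | Power (CRR 0.40) |
|---|---|---|---|
| 66 | 20 | 0.0242 | 0.904 |
| 48 | 20 | 0.0005 | 0.458 |
| 49 | 20 | 0.0007 | 0.504 |
| 48 | 16 | 0.0189 | 0.833 |
| 49 | 16 | 0.0226 | 0.851 |
| 48 | 15 | 0.0372 | 0.878 |
| 49 | 15 | 0.0429 | 0.889 |

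The stated 90% power is reproduced at n = 66. The attained alpha of 0.0242 fits the stated two-sided 0.05 read as one-sided 0.025. On that reading, 16 is the smallest cut-off that qualifies at either size. The required response proportion is 20/66 = 30.3% as planned, against 16/48 = 33.3% or 16/49 = 32.7%. Most of the power loss at a cut-off of 20 comes from leaving the cut-off unadjusted: moving to 16 restores power to 0.833 or 0.851.

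**4. What the interim data do to a new cut-off.** Take the first-stage count as fixed at 6 of 22, and assume no later responses informed the closure. The conditional type I error is P(X2 ≥ r − 6) at CRR 0.20:

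- Planned 20 of 66: 0.0436
- 16 of 48: 0.0232; 16 of 49: 0.0304 (both within the planned rule's value)
- 15 of 48: 0.0592; 15 of 49: 0.0737 (both above it)

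**5. Can Protocol section 9.4 replace SAP section 7?** It requires all patients to have six months of follow-up after first documented response. At the interim the all-DLBCL response rate was 57.1% (Protocol section 2.2), so 100 − 57.1 = 42.9% had no response to count from. Read literally, that condition cannot be met either.

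**The case against.** The strongest reply is that this is untidied text and not an invalid analysis. The SAP discloses the termination, the non-enrolment and the reduced totals, so a reader can see that the cohort is empty. SAP sections 5 and 5.9.1 still report CRR with exact 95% intervals by IRC and by investigator for every treated cohort. The efficacy sections prescribe no hypothesis test. The snapshot wording is permissive, and analyses are also allowed when all patients complete the study. Cut-offs of 15 and 16 appear nowhere in the plan. Section 4.1 also speaks of a one-sided alternative with type I error 0.05, under which 15 would qualify.

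Much of this stands. No treated patient's result is lost, rewording cannot restore the primary claim, an unmet snapshot condition does not bar reporting, and 20 CRs among 48 or 49 patients is attainable. The re-derived cut-offs are illustrations only.

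It does not remove the defect. Disclosure elsewhere does not tell the analyst what to do with section 5.9, which still requires the empty analysis. Section 4.1 does say that the non-GCB hypothesis will be tested, and gives a rejection rule. The only other timing in section 7 is for follow-up analyses. The separate futility document cited in section 6 was not available for this review. It is dated 14 May 2021, before the 31 August 2021 amendment that closed the cohort.

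**Conclusion.** The concern holds and must be fixed. The Phase 2 primary analysis and its per-protocol repeat have 0 of 100 planned patients, and the null hypothesis of CRR at most 0.30 is untested. The retained accrual sentence implies 236 patients against a stated 136. The snapshot condition is 17 or 18 patients short. The non-GCB rule has its stated power only at 66 patients: at 48 or 49, power at CRR 0.40 ranges from 0.458 to 0.889 across the cut-offs 15, 16 and 20, and the SAP does not say which applies.

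The zero count rests on the section 4 statement and the section 4.1 totals. The preference for 16 over 15 rests on reading alpha as one-sided 0.025. The conditional figures rest on the first-stage count staying at 6 and on no later responses having informed the closure. The primary row of the SAP section 3 table is blank in the text available, and nothing here depends on it.

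**What to change.** 1. **Section 5.9:** state that the Phase 2 primary analysis and its per-protocol repeat are not performed because the every-cycle cohort was not enrolled, and that the null hypothesis of CRR at most 0.30 is untested.
2. **Sections 4, 4.1 and 6:** delete the sentence on accruing about 100 patients, and mark the rest of the every-cycle design text as not implemented.
3. **Section 4.1, non-GCB:** label the hypothesis secondary, state that the 20-of-66 rule does not apply at 48 or 49, and present CRR with exact 95% intervals as descriptive. If the sponsor prefers a re-derived cut-off, such as 16 of 48 or 49, give its exact alpha and power and say that it was set after the April 2021 interim data were seen.
4. **Section 7:** replace the 66-patient condition with one the treated patients can meet. One option has two parts. Every treated responder has six months of follow-up after first response, or has progressed, died or left the study (including through its discontinuation). Every other treated patient has progressed, died, left the study or reached a stated minimum follow-up from first dose. Do not copy Protocol section 9.4.
5. **Clean-up:** give one non-GCB count (49 fits the totals of 89 and 136), and record these changes in section 4.3, including the reduction from 243 to 136.

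The cost is SAP wording only, with no new data or analyses. The sponsor would have to state openly that Phase 2 has no tested primary hypothesis.
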